	
• Proportion of subjects achieving a response of 30%, 50%, and 75% reductions from Baseline (D1) in mean NPRS average pain score in the affected leg at W2 and W4.• The mean change from Baseline (D1) to W2, W4, W8, and W12 in the mean NPRS average pain score in the lower back.• PGIC at W2, W4, W8, and W12.• CGIC at W2, W4, W8, and W12.• Cumulative use of rescue medication (mg of acetaminophen) through W4 and W12.• Time to first rescue medication dose.• Proportion of subjects requiring rescue medications.
Safety Endpoints:	
• AEs, compared between 4 groups receiving 1 SP-102 injection, 2 SP-102 injections, placebo followed by SP-102 repeat injection, or placebo only.• Change from Baseline (D1) in laboratory parameters.• Change from Baseline (D1) in vital signs.• Change from Baseline (D1) in neurological examination.
Statistical Analyses:	 The content of this table cell is completely redacted with black boxes.

	
[REDACTED]
 
Safety summaries will be provided for proportion of subjects experiencing AEs, clinical laboratory evaluations, vital sign measurements, and neurological examinations.
 
No interim analysis is planned for this study. Note that the study will be unblinded and the primary analysis will be completed after all subjects complete the 12-week assessments and data are cleaned. Subjects in the OL safety extension portion of the study will continue through W24. No efficacy data in the first 12 weeks of the study will change after the primary analysis is completed.

--	--

TABLE OF CONTENTS

SIGNATURE PAGE	2
SUMMARY OF CHANGES incorporated with AMENDMENT 3	3
SUMMARY OF CHANGES incorporated with AMENDMENT 2	4
SUMMARY OF CHANGES incorporated with AMENDMENT 1	5
SYNOPSIS.....	6
TABLE OF CONTENTS.....	14
LIST OF ABBREVIATIONS AND DEFINITIONS OF TERMS.....	19
1 INTRODUCTION	23
1.1 Background.....	23
1.1.1 Lumbosacral Radicular Pain.....	23
[REDACTED].....	
1.1.3 SP-102.....	25
1.2 Preclinical Studies.....	25
1.3 Clinical Studies.....	26
[REDACTED].....	
1.5 Study Rationale.....	27
1.6 Dose Rationale.....	27
1.7 Study Endpoint Rationale.....	28
1.8 Risks and Benefits for Subjects	28
2 STUDY OBJECTIVES.....	30
2.1 Primary Objective	30
2.2 Secondary Objectives.....	30
3 INVESTIGATIONAL PLAN.....	31
3.1 Overall Study Design and Plan.....	31
3.2 Study Duration.....	33
3.3 Selection of Study Population.....	33
3.3.1 Inclusion Criteria	33

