3.4.8.2 Prior and Concomitant Medications

All prescription and non-prescription medications (eg, over-the-counter drugs and herbal supplements) that subjects report taking during the 30 days prior to the Screening Visit will be assessed and recorded in the eCRF Concomitant Medication. For each medication, documentation should list the trade or generic name, the total daily dose including units (or the dose, units and scheduled and actual frequency of administration if the medication is not taken daily), the route of administration, and the reason for use.

Concomitant medication refers to all drugs and therapies used from the time of informed consent through the EOS participation. For D1 to Week 12, rescue medication (acetaminophen) use will be recorded only in the eDiary by the subject. After W12, when the eDiary is returned to the clinic, subjects will report acetaminophen use to study staff, and reported use will be documented in the Concomitant Medication eCRF.

[Redacted]

Changes, additions, or discontinuations to medications will be assessed and recorded in the eCRF during each study visit and at the EOS/ET Visit (D169). All as needed (*pro re nata*, *PRN*) prescriptions should be converted to reflect actual number of pills and dose taken per day.

To be eligible for this study, each subject agrees that any oral, non-opioid analgesic medication regimen for or indications other than radiculopathy pain (eg, neuropathic pain, cardiac prophylaxis) will not be altered from the Screening Visit through W12. The Investigator must inform the Medical Monitor (in advance, if possible) if a subject requires analgesic medications contrary to the protocol during the study.

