3.5.6.2 Clinical and Patient Global Impression Scales

The CGIS ([Appendix I](#)) is rated on an 8-point scale, with responses ranging of responses from 0 (not assessed) and 1 (normal) through 7 (amongst the most severely ill subjects) (to be completed prior to IP administration at the Baseline (D1) Visit). The CGIC ([Appendix I](#)) scores

range from 0 (not assessed) and 1 (very much improved) through 7 (very much worse) as determined by the trained site rater. The PGIC scores range from 1 (very much improved) through 7 (very much worse) as assessed by the subject. The CGIC and PGIC are obtained at each clinic visit following Baseline (D1).

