**7.12.6.12 CGIC at Week 2, Week 4, Week 8, and Week 12.**

The CGIC is an 8-point scale (0 to 7, where 0 is not assessed, 1 is very much improved, and 7 is very much worse) that allows clinicians to rate the subject's global impression of change. CGIC will be collected after randomization at Weeks 2, 4, 8, 12, 16, 20, and 24. For analysis, a subject will be classified as either CGIC responder, that is, a CGIC response of 1: very much improved or 2: much improved or a CGIC non-responder, that is, all other CGIC responses (recorded as 3-7 in the scale). Subjects who do not complete the measure at the timepoint of interest will also be considered non-responders. The number and percentage of subjects reporting each of the seven

CGIC response levels will also be summarized by visit and treatment. Analyses will utilize separate Chi-Square tests for Week 2 and Week 4 where the p-value of the treatment difference will be presented. Separate logistic regression models with treatment, site, and Pain Catastrophizing Scale group ( $<30$  or  $\geq 30$ ) as factors will also be used to compare the treatment groups for Week 2 and Week 4 using the 2 treatment groups. The odds ratio of SP-102 vs placebo at Weeks 2 and 4, and its corresponding 95% CI and p-value will be presented. Listings of CGIC will also be provided.

Separate Chi-Square tests and similar logistic regression analyses will be applied at Weeks 2, 4, 8, and 12 using the treatment group with four arms: SP-102/SP-102, PBO/SP-102, SP-102/none, PBO/none. The following odds ratios at Weeks 2, 4, 8, and 12 and the corresponding 95% CIs and p-values will be presented:

- SP-102/none vs. PBO/none
- SP-102/SP-102 vs. PBO/none
- SP-102/none vs. PBO/SP-102
- SP-102/SP-102 vs. PBO/SP-102

A summary of the assessments at Weeks 16, 20, and 24 will be presented.

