#### **7.12.6.13 Cumulative use of rescue medication (mg of acetaminophen)**

In this study, acetaminophen is the permitted and study-provided rescue medication. For subjects that withdraw early, their missing weekly values after withdrawal will be imputed using the average weekly score for the respective treatment group. If the subject has partial records of rescue medication on the week of subject's withdrawal, the rescue medication use on that week will be imputed as follows:

[ partial record of rescue medication on the withdrawal week \* (7/number of days in the withdrawal week with partial record) ].

Cumulative use of rescue medication at Week 4 will be obtained as the rescue medication use during the first four weeks relative to the index injection, that is, up to the subject's Day 29 in the study. It will be analyzed using an analysis of variance (ANOVA) model with cumulative use from baseline to Week 4 as the response variable with fixed effects for treatment (two groups: SP102 or placebo), site, and Pain Catastrophizing Scale group ( $<30$  or  $\geq 30$ ). The same ANOVA model will

be applied on only subjects that complete 4 Weeks and output will be presented using the two treatment groups.

Cumulative use of rescue medication at Week 12 will be obtained as the rescue medication use during the first 12 weeks relative to the index injection, that is, up to subject's Day 85 in the study. It will also be analyzed using an ANOVA model with cumulative use from baseline to Week 12 as the response variable with fixed effects using the four treatment (SP-102/SP-102, PBO/SP-102, SP-102/none, PBO/none) variable, site, and Pain Catastrophizing Scale group (<30 or ≥30). The same ANOVA model will be applied on only subjects that complete 12 Weeks and output will be presented using the four treatment groups.

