#### **7.12.6.16 Percent of rescue medication free days.**

The percent of rescue medication free days will be calculated for the primary efficacy endpoint completers as:

$$\frac{\text{Number of days without rescue medication from baseline to subject's Day 29th in the study}}{28} \times 100$$

For subjects that withdrew from the study prior to the subject's Day 29th in the study, the percent of rescue medication free days will be calculated as:

$$\frac{\text{Number of days without rescue medication from baseline to Early Termination Date}}{\text{Number of days from baseline to Early Termination Date}} \times 100$$

This will be analyzed for the primary analysis period. A one-way ANOVA model will be used to test the difference between SP-102 and the placebo arms.

**7.12.6.17 The mean change from Baseline (D1) to Week 2, Week 4, Week 8, and Week 12 in the mean morning (AM) NPRS average pain score in the affected leg**

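### The cumulative-rescue ANOVA omits recorded pre-injection acetaminophen use, and the CGIC model omits the D1 CGIS: a modest, cheaply recovered loss of efficiency, without bias

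*Protocol*

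**What the plan says.** **Rescue use.** The protocol synopsis, under Efficacy Endpoints, names "Cumulative use of rescue medication (mg of acetaminophen) through W4 and W12" among the other secondary endpoints. For Week 4, SAP 7.12.6.13 states: "It will be analyzed using an analysis of variance (ANOVA) model with cumulative use from baseline to Week 4 as the response variable". The model terms are the two treatment groups, site and PCS group. The Week 12 model has "fixed effects using the four treatment (SP-102/SP-102, PBO/SP-102, SP-102/none, PBO/none) variable, site, and Pain Catastrophizing Scale group". Time to first rescue (SAP 7.12.6.14) is analysed like another time-to-event endpoint. The section cited there, 7.11.6.2, evidently means 7.12.6.2, where the Cox model adjusts for site and PCS. For percent of rescue-free days, SAP 7.12.6.16 says: "A one-way ANOVA model will be used to test the difference between SP-102 and the placebo arms". None of these contains a pre-injection acetaminophen term.

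**CGIC.** SAP 7.12.6.12 uses chi-square tests and also "Separate logistic regression models with treatment, site, and Pain Catastrophizing Scale group", reporting odds ratios with 95% confidence intervals. CGIS does not appear.

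**What is collected before injection.** Protocol 3.4.8.2 covers prescription and non-prescription medications "that subjects report taking during the 30 days prior to the Screening Visit will be assessed and recorded in the eCRF Concomitant Medication", with the daily dose or the dose and actual frequency. It also covers all drugs used from consent onward. From D1 to Week 12, acetaminophen goes into the eDiary only. Protocol 3.5.6.2 describes the CGIS as "to be completed prior to IP administration at the Baseline (D1) Visit".

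**Practice elsewhere in the SAP.** The Week 4 models for ODI (7.12.5), PainDETECT (7.12.6.8) and BPI-SF (7.12.6.9) include the baseline score. The logistic model for NPRS responders (7.12.6.10) includes baseline leg pain.

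**The concern.** Subjects who used much acetaminophen before the trial are likely to use more of it afterwards. If that persistent difference is not modelled, it stays in the residual variance of cumulative mg, so the comparison is less precise than the collected data allow and a chance imbalance in habitual use goes unadjusted. Similarly, a rating of improvement may depend on how severe the clinician judged the condition to be at the start, and the CGIC model ignores that rating.

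The SAP adjusts for baseline on its other scale endpoints, and no visible text explains why these two differ. What is at stake is efficiency on other secondary endpoints, not the validity of the primary result.

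**Working it through.** **The plan's own figure.** The only visible sizing figure is about 400 randomized with 332 completing Week 4 (Protocol synopsis). 332/400 = 0.83, which implies a 17% allowance. The sample-size assumptions are redacted, so 332 cannot be rebuilt. No power or precision is visible for rescue use or CGIC. Below, n = 332/2 = 166 per arm, two-sided alpha 0.05.

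**1. Cumulative mg (linear model).**
- Without the covariate, the 95% half-width in SD units is 1.96 × sqrt(2/166) = 0.215.
- With it, the standard error is multiplied by sqrt(1 - r^2). Here r is the correlation between cumulative mg and the baseline term as entered, given site and PCS group.
- Equivalent extra subjects = 332/(1 - r^2) - 332.
- The last column takes a contrast with 80% power before adjustment.

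| r (assumed) | SE factor | SE reduction | Half-width (SD) | Extra subjects on 332 | Power, from 80% |
|---|---|---|---|---|---|
| 0.1 | 0.995 | 0.5% | 0.214 | 3 | 80.4% |
| 0.2 | 0.980 | 2.0% | 0.211 | 14 | 81.6% |
| 0.3 | 0.954 | 4.6% | 0.205 | 33 | 83.6% |
| 0.5 | 0.866 | 13.4% | 0.186 | 111 | 89.9% |

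**2. CGIC (logistic model, odds ratio).** Simulation of 600 trials per scenario, 166 per arm. Assumed inputs: intercept -0.85, treatment log odds ratio 0.65, and one standardized D1 covariate. Site and PCS were left out for simplicity.

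| Covariate log OR per SD | log OR, without → with | SE, without → with | SE ratio | Power, without → with |
|---|---|---|---|---|
| 0.3 | 0.637 → 0.652 | 0.231 → 0.234 | 1.015 | 79.0% → 81.2% |
| 0.5 | 0.631 → 0.667 | 0.230 → 0.238 | 1.033 | 79.2% → 80.7% |
| 1.0 | 0.544 → 0.654 | 0.228 → 0.252 | 1.106 | 65.5% → 76.0% |
| 1.5 | 0.468 → 0.664 | 0.226 → 0.272 | 1.203 | 57.7% → 68.5% |

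The interval for the log odds ratio gets wider, not narrower. The odds ratio is non-collapsible: conditioning on a prognostic covariate moves the estimate away from zero by more than it enlarges the standard error, so power rises. A narrower interval appears only for a standardized risk difference (SE factors 0.993, 0.976, 0.917 and 0.848 in the same scenarios), which the SAP does not plan to report.

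**3. Time to first rescue (Cox model).** Simulation of 300 trials per scenario, 166 per arm. Assumed inputs: treatment log hazard ratio -0.35 and censoring at 28 days. The SE ratio with versus without the covariate is 1.003, 1.005 and 1.008 for covariate log hazard ratios of 0.3, 0.5 and 1.0. Again the interval does not narrow. The estimate moves away from zero, and power rises when the covariate is clearly prognostic.

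**The case against.** The strongest case is that this is a preference and not an error. Leaving out a covariate does not bias a randomized comparison, these are other secondary endpoints, and no document gives the correlation on which the gain depends.

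The correlation may well be small. The outcome is study-provided rescue that the subject enters in the eDiary, while the proposed baseline is a medication history in the eCRF. Some subjects must stop opioids before Screening, so their earlier acetaminophen use may reflect a different regimen. The rescue, prohibited-medication and allowed-medication sections are redacted, so any limit on acetaminophen during screening cannot be seen. All of this stands, and it is why the low end of the range is shown. It does not remove the point: a term built from data already collected costs one degree of freedom, and the SAP already derives prior opioid use from medication records for a sensitivity model (7.12.3).

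A reader might infer more in three ways, none of them supported:
- *That both models lack the baseline of the same measure.* CGIC rates change and has no pre-injection value. CGIS is a separate severity scale that can serve as a covariate.
- *That all the intervals are wider than they need be.* That follows only for the linear cumulative-mg model. For the odds ratio and the hazard ratio the loss is in power.
- *That the printed rescue interval is therefore too wide overall.* SAP 7.12.6.13 fills weeks after withdrawal with the treatment-group mean, which understates the standard error. If whole values were imputed for a share m, the naive standard error would be (1 - m) times the correct one: 0.95 at 5% and 0.83 at 17%. The latter is an upper illustration, since only weeks after withdrawal are filled. This is a separate problem, and the covariate does not repair it.

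**Conclusion.** The point holds as a minor efficiency improvement. The cumulative-rescue ANOVA has no pre-injection acetaminophen term and the CGIC model has no D1 CGIS, although both are recorded.

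For cumulative mg, the standard error would fall by 0.5% to 13% for r between 0.1 and 0.5. That r is an assumption the documents do not supply, and the difference in source between baseline and outcome argues for the lower part of the range. For CGIC and time to first rescue the expected gain is power, of a size that depends on how prognostic the covariate is, and the estimate becomes conditional on the covariate.

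The two-arm comparison is unbiased with or without the change. The 12-week four-group comparison depends on who received a repeat injection; it is not a randomized contrast, and nothing here alters that.

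**What to change.** Amend the SAP before unblinding.

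1. **Main change (7.12.6.13).** Derive mean daily acetaminophen (mg) before the index injection from the medication eCRF, with 0 if none is recorded. State the averaging window and how combination products are counted. Add log(1 + mg/day) to the cumulative-rescue model, which becomes an ANCOVA.
2. **Optional (7.12.6.14).** Add the same term to the Cox model for time to first rescue, and state that the hazard ratio is then conditional on it.
3. **Optional (7.12.6.12).** Add D1 CGIS to the CGIC logistic models, treating a score of 0 (not assessed) as missing, and describe it as a related severity rating. State that the odds ratio is conditional and that the aim is power.

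The cost is SAP wording, one derived variable and one degree of freedom per model. No new data are collected and study conduct does not change. The group-mean imputation in 7.12.6.13 needs its own correction.

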α	alpha
μg	microgram
μmol	micromole
ADR	adverse drug reaction
AE	adverse event
AESI	adverse event of special interest
ALT (SGPT)	alanine aminotransferase (serum glutamic pyruvic transaminase)
AST (SGOT)	aspartate aminotransferase (serum glutamic oxaloacetic transaminase)
BMI	body mass index
BPI-SF	Brief Pain Inventory-Short Form
bpm	beats per minute
C	Celsius
CDISC	Clinical Data Interchange Standards Consortium
CD/UT	cognitive debrief and usability testing
CFR	Code of Federal Regulations
CGI	Clinical Global Impression
CGIC	Clinical Global Impression of Change
CGIS	Clinical Global Impression-Severity
C_{max}	maximum concentration
CRA	clinical research associate
CRO	contract research organization
CSF	cerebrospinal fluid
CV	coefficient of variation
D	day
DAL	Daily Acetaminophen Log
DB	double-blind
DDE	direct data entry
ECG	electrocardiogram
eCOA	electronic clinical outcome assessment
eCRF	electronic case report form
EOS	end of study
ESI	epidural steroid injection
ET	early termination

Abbreviation	Definition
F	Fahrenheit
FAERS	FDA Adverse Event Reporting System
FDA	Food and Drug Administration
FSH	follicle stimulating hormone
g	gram
GCP	Good Clinical Practice
HADS	Hospital Anxiety and Depression Scale
HbA1c	Hemoglobin A1c
HIV	human immunodeficiency virus
IB	Investigator's Brochure
ICF	informed consent form
ICH	International Council on Harmonisation
IEC	independent ethics committee
█	█
IND	Investigational New Drug
INR	International Normalization Ratio
IP	investigational product
IRB	institutional review board
IUD	intrauterine device
IWRS	interactive web recognition system
LFT	liver function tests
MEDD	Mean Equivalent Daily Dose
MedDRA	Medical Dictionary for Regulatory Activities
mITT	Modified intent-to-treat (dataset)
mg	milligram
min	minutes
mIU	milli international unit
mL	milliliter
mm	millimeter
mmHg	millimeters of mercury
MMRM	mixed model for repeated measures
MRI	magnetic resonance imaging
mRNA	messenger ribonucleic acid
NPRS	Numeric Pain Rating Scale

Abbreviation	Definition
NSAID	nonsteroidal anti-inflammatory drug(s)
ODI	Oswestry Disability Index
OL	open-label
PCS	Pain Catastrophizing Scale
PGIC	Patient Global Impression of Change
po	given by mouth
PP	per-protocol (dataset)
PT	prothrombin time
PTT	partial prothrombin time
REML	restricted maximum likelihood
RLD	Reference Listed Drug
SAE	serious adverse event
SAP	statistical analysis plan
SD	standard deviation
SDTM	Study Data Tabulation Model
SOP	standard operating procedure
TEAE	treatment emergent adverse event
TF	transforaminal(ly)
T _{max}	time to maximum concentration
US	United States
V	visit
W	week
WBC	white blood cells

ADMINISTRATIVE STRUCTURE

The Study Team Contact list is provided in a separate document.

1 INTRODUCTION

1.1 Background

1.1.1 Lumbosacral Radicular Pain

Back pain is a widespread, debilitating disorder that results in an enormous socioeconomic burden. The lifetime prevalence of low back pain ranges from 60% to 90%, and the annual incidence is ~5% (Frymoyer-1988, Frymoyer-1992). The annual cost to treat back pain has been estimated to exceed \$100 billion, of which it is estimated that up to \$50 billion is due to lost productivity (Cleeland-1989).

A specific type of back pain in the distribution of lumbosacral nerves is known as lumbosacral radicular pain, which is frequently referred to as sciatica. It is a common condition with a lifetime incidence varying from 13% to 40% (Stafford-2007). The corresponding annual incidence of an episode of lumbosacral radicular pain ranges from 1% to 5% (Frymoyer-1988, Frymoyer-1992). It is rarely diagnosed before the age of 20, peaks in incidence in the fifth decade of life and declines thereafter (Frymoyer-1992).

Lumbosacral radicular pain is believed to result most commonly from prolapsed disc material causing pain secondary to mechanical impingement and/or inflammation of the anterior primary rami of lumbar nerve roots. Histological changes have been first described in 1951 (Lindahl-1951). Approximately 90% of cases of lumbosacral radicular pain are caused by a herniated disc with nerve root compression, with various other etiologies accounting for the remaining 10% of the cases (Stafford-2007, Valat-2010).

There are several conservative treatments for lumbosacral radicular pain, each with varying levels of effectiveness. These therapeutic approaches include bed rest, staying active (in contrast to bed rest), analgesic or non-steroidal anti-inflammatory drugs (NSAIDs), acupuncture, spinal manipulations, traction therapy, physical therapy, behavioral treatment, and epidural steroid injections (ESIs) (Frymoyer-1992, Koes-2007, Valat-2010). The initial phase of sciatica frequently responds to conservative management with no intervention. For example, in a study of more than 208 subjects with obvious symptoms and signs of a lumbosacral radicular pain (5th lumbar vertebra and 1st sacral vertebra), treated with nonsteroidal anti-inflammatory drug piroxicam or placebo, 70% in active group reported a marked reduction in back and leg pain and improved functionality within 4 weeks and 60% had returned to work at that point in time. However, approximately 30% of subjects in both groups still complained of back pain and 19.5% were out of work after 1 year (Weber-1993). When these more conservative treatments for lumbosacral radicular pain are ineffective, ESIs or surgical interventions are commonly used.

[REDACTED]

[REDACTED]

[REDACTED]

[REDACTED]

[REDACTED]

[REDACTED]

[Redacted]

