
Planned Sample Size:
	
Approximately 400 subjects will be randomized in this study. The sample size goal of this study is for 332 subjects to complete W4.

Key Subject Selection Criteria:
	
Inclusion Criteria: Screening Visit Inclusion Criteria (D-22 to D-8)
 
 1. Able and willing to read, write, and understand the English language and provide English-language written informed consent prior to beginning any study procedures. 2. Age 18 to 70 years (inclusive) at the Screening Visit. 3. A diagnosis of lumbosacral radicular pain at the Screening Visit. 
[REDACTED]

	
 [REDACTED] [REDACTED] [REDACTED] [REDACTED] [REDACTED] [REDACTED] [REDACTED] [REDACTED] [REDACTED] 
10. If sexually active and a female of childbearing potential or a male capable of bearing a child, agrees to use an effective method of birth control during the study. [REDACTED]
 
 [REDACTED] [REDACTED] [REDACTED] [REDACTED] [REDACTED] 
12. Reviewed all study-specific educational materials and has, in the opinion of the Investigator, the cognitive abilities to understand and appropriately complete all study-mandated procedures.
 
 [REDACTED] [REDACTED]
--	--

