3.4.3 Treatment Assignment

Using an Interactive Web Response System (IWRS), on D1, the site staff or research pharmacist will contact the IWRS after the Investigator has confirmed that the subject fulfills all the inclusion/exclusion criteria. The IWRS will assign a randomization number to the subject, which will be used to link the subject to a treatment arm. The research pharmacist will prepare the appropriate IP and deliver it to study staff in preparation for injection.

A randomization schedule will be employed to facilitate effective randomization and allocation concealment. The schedule will involve a block randomization technique, randomly assigning participants within blocks based on a 1:1 allocation ratio. The randomization schedule will be stratified by study site.

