## 7.12 Efficacy Analyses

All statistical tests will be performed using a two-tailed 5% overall significance level, unless otherwise stated. All comparisons between treatments will be reported with 95% confidence intervals (CI) for the difference. Pain profiles through the first four weeks will be presented by the treatment received for the first injection (SP-102, Placebo). Moreover, pain profiles through 12 weeks will be presented by treatment received for second injection (SP-102/SP-102, PBO/SP-102, SP-102/none, PBO/none). Also, the ‘site’ indicated in this section refers to the final pooled sites as described in [Section 7.2.10](#).

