### 7.12.3 Sensitivity Analysis

The following sensitivity analysis will be applied;

1. The primary analysis will be re-run for the PP Population.
2. The primary analysis model will be re-run but will include sex, duration of leg pain, prior opioid use for current episode of pain (yes/no) as additional factors in the model. Prior opioid use for current episode of pain will be determined by reviewing all the subject's medications and checking if there is any medication with opioid (using the ATC3 codes as listed below) and comparing the medication's start date and end date to the current episode date, that is, for the subject to be classified as having a prior opioid use for current episode of pain ('yes'), the current episode date should be within the medication's start date and end date:

- N02A (Opioids)
- A07D (Antipropulsives)
- R05D (Cough suppressants, excl. combinations with expectorants)
- R05F (Cough suppressants and expectorants, combinations)

Duration of leg pain is the number of months from start date of current episode of lumbosacral radicular pain to D1. That is,

[ D1 visit date – start date of current episode of lumbosacral radicular pain + 1 ] / 30.

The following SAS codes will be used to implement the placebo-based pattern mixture imputation.

[REDACTED]

The imputed data sets will be analyzed with the same MMRM model employed in the primary analysis and then summarized using PROC MIANALYZE.

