#### **7.12.5 Key Secondary Analysis**

Baseline ODI is defined as the last ODI assessment score prior to the first injection on D1. The change in ODI total score from baseline will be analyzed using the mITT and PP Analysis Populations. This endpoint will be analyzed using the analysis of covariance (ANCOVA) model where change from baseline in ODI score at Week 4 will be the response variable with fixed effects for treatment (two groups: SP-102 or placebo), site, Pain Catastrophizing Scale group (<30 or

≥30), and baseline ODI. The treatment group categories for this analysis will be the SP-102 and placebo groups. A summary of the observed and change from baseline ODI total score will be presented by visit and treatment group jointly for both the primary and secondary analysis periods. Listings of all 10 topic scores and total scores will be presented.

The following SAS code will be used for this key secondary analysis;

[REDACTED]

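### Duration of the current leg-pain episode is derived but enters only a sensitivity re-run, so the primary and Week 4 ODI tests may lose a modest amount of precision

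*Protocol*

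**What the plan says.** **Background.** Protocol 1.1.1 states: "The initial phase of sciatica frequently responds to conservative management with no intervention". It then cites a piroxicam trial in which 70% of the active group had marked relief within 4 weeks, while about 30% of both groups still had back pain at 1 year. It reports no outcome by time since onset.

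**Primary endpoint.** The text of the primary model is redacted. SAP 7.12.3, item 2, says: "The primary analysis model will be re-run but will include sex, duration of leg pain", together with prior opioid use, as factors added to that model. Duration is therefore not in the primary model itself. The 12-week model in SAP 7.12.6.4, described as similar to the primary one, lists treatment, week, site, Pain Catastrophizing Scale (PCS) group, baseline leg pain and treatment-by-week, with no duration term.

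**Definition.** "Duration of leg pain is the number of months from start date of current episode of lumbosacral radicular pain to D1". The variable is continuous and fixed before the injection.

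**Key secondary endpoint.** The Week 4 ODI ANCOVA in SAP 7.12.5 has "fixed effects for treatment (two groups: SP-102 or placebo), site, Pain Catastrophizing Scale group", plus baseline ODI. No visible ODI analysis includes duration.

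**Testing order.** Under SAP 7.12.6.19 the ODI test opens only if the primary test is significant, and the remaining secondary tests open only after ODI.

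**The concern.** If time since onset predicts how much a subject improves over 4 weeks whatever the injection, a model without it leaves that variation in the residual. The primary contrast (SAP 7.12.2) averages four weekly means. This reduces within-subject noise and leaves relatively more of the between-subject variation that a baseline covariate can explain. The SAP already adjusts its visible efficacy models for one baseline characteristic of this kind, PCS group, and it singles out duration as one of only three covariates worth adding in a sensitivity analysis.

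What is at stake is efficiency in the two tests on which every later test depends. The sensitivity re-run cannot make up for it. Its p-value opens nothing in the sequence, it adds three covariates at once so the contribution of duration is not isolated, and it does not cover ODI.

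**Working it through.** **Inputs from the documents**
- Significance level: "All statistical tests will be performed using a two-tailed 5% overall significance level, unless otherwise stated" (SAP 7.12).
- Target: "The sample size goal of this study is for 332 subjects to complete W4"; and "Approximately 400 subjects will be randomized in this study" (Protocol synopsis).
- Allocation: "randomly assigning participants within blocks based on a 1:1 allocation ratio" (Protocol 3.4.3). Hence 332/2 = 166 per arm.

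**The plan's own figure.** The 332 cannot be rebuilt, because the sample-size sections (Protocol 5.2.1, SAP 5) are redacted. The only available check is 1 − 332/400 = 17.0%, the loss that would link the two numbers. That percentage is back-calculated and stated nowhere visible.

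**Assumptions**
- R² is the share of residual variance that duration explains after the covariates already in the model. The documents give no value, so a range is shown.
- Base power is taken as 90%, with 80% as a check. Neither figure is visible in the documents.

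**Formulas**
- Ratio of standard errors = √(1 − R²).
- Equivalent number of subjects = 332/(1 − R²).
- Power after adjustment = Φ[(1.960 + 1.282)/√(1 − R²) − 1.960], where 1.282 is the normal quantile for 90% power.

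Example at R² = 5%: √0.95 = 0.975, so the standard error falls 2.5%; 332/0.95 = 349.5; power = Φ(3.242/0.975 − 1.960) = Φ(1.366) = 91.4%.

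| Assumed partial R² | Fall in SE | Equivalent N (332 without duration) | Power, from 90% |
|---|---|---|---|
| 0% | none | 332 | about 89.9% |
| 1% | 0.5% | 335 | 90.3% |
| 3% | 1.5% | 342 | 90.8% |
| 5% | 2.5% | 349 | 91.4% |
| 10% | 5.1% | 369 | 92.7% |

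The 0% row carries the cost of the extra parameter. With about 322 residual degrees of freedom (332 − 10, the 10 being an allowance for model terms), the variance rises by 1/322 = 0.3%, and about 0.1 power point is lost. The other rows do not deduct this cost, which would lower each by about the same 0.1 point.

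**Check from 80% power.** With partial correlation r, so that R² = r²:
- r = 0.1 (R² = 1%) gives 80.4%.
- r = 0.2 (4%) gives 81.6%.
- r = 0.3 (9%) gives 83.6%.

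A gain of 2 power points needs r of about 0.23 from 80% (R² about 5%) or about 0.27 from 90% (R² about 7%).

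**Chance imbalance.** The standard error of the treatment difference is √(2/166) = 0.110 outcome SD. At R² = 5%, r = √0.05 = 0.224, so chance imbalance in duration moves the unadjusted estimate by 0.224 × 0.110 = 0.0245 SD (one standard deviation), or about 22% of one standard error. This shift is already part of that standard error. It restates the precision loss and is not a second effect.

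**The case against.** The strongest case against is that the documents never show duration to be prognostic. A reader might infer from Protocol 1.1.1 that they do, since it speaks of recovery without intervention and of marked relief within 4 weeks, the primary horizon. The text does not support that. It compares no early and late cases, and the 70% is the active piroxicam group, so it measures neither untreated recovery nor a gradient by duration. The same section places epidural steroid injection after conservative treatment has failed, so the sentence about the initial phase need not describe these subjects. Most inclusion criteria are redacted. If they restrict episode duration, its spread and its explanatory value could be small. All of this stands, and it limits the claim to precision that may be lost.

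A reader might also infer that chance imbalance in duration biases the deciding estimates. It does not: randomisation protects the comparison and the type I error rate.

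It can further be said that the pre-specified re-run already shows whether adjustment moves the primary estimate, and that keeping an unquantified covariate out of the main model is a legitimate choice. The first part is correct for the primary endpoint only. The second is fair, but the balance favours inclusion: about 0.1 power point is at risk if duration is uninformative, against 2.5 to 3.6 points gained at r = 0.3.

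Finally, this would change a protocol-planned analysis and so needs more than an edited model statement. True, but SAP section 11 exists to record such changes.

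**Conclusion.** The point holds as a modest efficiency improvement, not as a demonstrated loss. What the documents establish is that duration is derived, is fixed before injection, and enters neither the primary model nor the Week 4 ODI ANCOVA. The first of these rests on the wording of the sensitivity analysis, because the model text is redacted.

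The size rests on two assumptions, partial R² and base power. For R² between 1% and 5% the gain from 90% power is 0.3 to 1.4 points; at 10% it is 2.7 points. Duration is a baseline variable and the models are linear, so adding it leaves the target treatment difference unchanged. The change is worth making because it costs almost nothing and serves the two tests that gate all others. The trial would remain valid without it.

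**What to change.** Before unblinding:

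1. Add duration of the current episode as a continuous covariate, with its form fixed in advance, to the primary MMRM and to the Week 4 ODI ANCOVA. Log months is one reasonable form, since a linear term in a possibly skewed number of months may capture little. The SAP formula, (D1 − onset + 1)/30, gives at least 1/30 for any onset on or before D1, so the logarithm is always defined.
2. Keep the re-run with sex and prior opioid use as the sensitivity analysis, now added on top of the duration-adjusted model.
3. Add a rule for partial onset dates covering both a missing day and a missing month, for example the midpoint of the possible interval, capped at D1. The visible rules in SAP 7.3.5 cover only adverse events and concomitant medications, and without such a rule subjects could drop out of the model. The planned sensitivity analysis needs this rule in any case.
4. Record the change in SAP section 11, and state there that the expected gain is an assumption.

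The cost is about one degree of freedom per model and some SAP wording. No new data are collected.
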